As demonstrated in the PoC Study CCFZ533X2203 in pSS, a single s.c. dose of 600 mg iscalimab at Day 1 will deliver plasma concentrations generally above 40 µg/mL after 1 week. Subsequent weekly doses on Week 61 and 62 in Arms 1 and 2 are expected (i) to maintain CFZ533 plasma levels above 40 µg/mL, and (ii) to deliver iscalimab trough levels that are close to expected steady state conditions.

Further supportive arguments on the selected loading dosing regimen are provided in the Rationale for dose/regimen and duration of treatment of the TWINSS core study protocol (refer to Section 4 of the core study protocol).

Rationale for maintenance regimen

The maintenance regimen of 600 mg s.c. Q2W is expected to provide a median steady state trough plasma level at about 144 µg/mL (90% of the population within 282 - 46 µg/mL), in the upper range of trough levels observed in the PoC Study CCFZ533X2203-Cohort 2 (i.v. regimen; these concentrations were associated with clinical efficacy and suppression of a biologically relevant biomarker CXCL13 - a marker of germinal center activity).

The maintenance regimen of 300 mg s.c. Q2W is expected to deliver a median steady state trough plasma level at about 54 µg/mL (90% of the population within 125 - 0.1 µg/mL), with a reasonable chance to show efficacy in SjS.

The between subject variability in exposure within the two treatment arms (to a lesser extent in the 600 mg treatment arm) is likely to depend on the biology of CD40 in target tissues (expression level, turnover) and its potential modulation during the treatment period.

Rationale for the duration of the safety follow-up period (target engagement after the last dose)

Based on predicted median CFZ533 plasma concentration-time profile at 600 mg s.c. Q2W regimen, at about 14 weeks after the last dose, iscalimab plasma concentrations are expected to drop below 20 µg/mL with no expected pharmacodynamic activity in target tissues (e.g., germinal centers; data from non-human primates - please see current IB).

A 12-week follow-up period (14 weeks after the last dose) has been selected for the study and is justified to monitor for any related serious adverse events (SAE).

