8.5.2 Pharmacokinetics

Free CFZ533 (iscalimab) plasma concentrations will be measured in all participants.

PK samples will be collected at the visits defined in the assessment schedule. All blood samples will be taken by either direct venipuncture or an indwelling cannula inserted in a forearm vein. Details of sample processing, handling, storage and shipment will be described in a separate laboratory manual.

All samples will be given a unique sample number and a dose reference identification number as listed in the [Section 16.5](#). The actual sample collection date and time will be entered on the appropriate eCRF.

Free CFZ533 (iscalimab) plasma concentrations will be determined using a validated target-based sandwich assay. The data and details of the analytical methods will be provided in a standalone Bioanalytical Data Report.

Concentrations below the lower limit of quantification (LLOQ) will be reported as “zero” and missing data will be labeled as such in the Bioanalytical Data Report.

For each PK sample, the actual recorded sampling time will be captured, and the elapsed time since the first and since the last dose will be calculated.

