12.5 Analysis of secondary endpoints/estimands

12.5.1 Pharmacokinetics

Trough free iscalimab plasma concentrations will be listed by treatment arm, subject, and visit/sampling time point.

Descriptive summary statistics will be provided by iscalimab dose level and analysis visits, including the frequency (n, %) of concentrations below the LLOQ. Summary statistics will include mean (arithmetic and geometric), SD, coefficient of variation (CV) (arithmetic and geometric), median, minimum and maximum.

Concentrations below LLOQ will be treated as zero in summary statistics.

The following PK parameters will be determined: trough concentration (C_{trough}), steady state (ss), and will be directly derived from the bioanalytical data (summary statistic tables; no non-compartmental analysis will be performed).

For each iscalimab concentration (or sample), an elapsed time since first (and last) dose of iscalimab will be calculated based on a Dose Reference ID (provided in the Blood Log). The time window for deriving the elapsed time will be defined in the SAP.

Graphical presentation of the data will be provided.

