Full Analysis Set (FAS): The FAS comprises all participants to whom study treatment for the extension study has been assigned by the re-assignment algorithm. For analysis on FAS, participants will be analyzed according to the treatment group to which they have been assigned. Only data in the extension study will be included in the analysis.

Summaries of extension data in FAS will be based on the core study cohort assignment and reassigned treatment groups.

- Cohort 1 CFZ533 600 mg
- Cohort 1- CFZ533 300 mg
- Cohort 2 CFZ533 600 mg
- Cohort 2 CFZ533 300 mg

Safety Set (SAF): The Safety Set includes all subjects who received at least one dose of study treatment. Subjects will be analyzed according to the actual treatment received. The safety set will be used in the analysis of all safety variables.

The actual treatment received in a period is defined as the treatment dose level (including loading dose) that a subject was most frequently exposed to during the period. The frequency will be calculated using data collected on the Dose Administration Record (DAR). In case a subject is exposed to more than one dose level for the same number of times during a period, the actual treatment is the earliest one administered to the subject in that period.

Summaries of extension data in SAF will be based on the re-assigned treatment groups.

- CFZ533 600 mg
- CFZ533 300 mg

The PK Set (PKS) includes all subjects who received at least one dose of iscalimab treatment and have quantifiable PK measurements of iscalimab. Analysis of plasma PK, will be based on PKS and by the iscalimab treatment dose level a subject is most frequently exposed to, including the loading dose, during the study. Only data in the extension study will be included in the analysis.

Summaries of extension data in PKS will be based on the re-assigned treatment groups.

- CFZ533 600 mg
- CFZ533 300 mg

The IM Set (IMS) includes all subjects who received at least one dose of iscalimab treatment and have quantifiable immunogenicity measurements of iscalimab. Analysis of immunogenicity data will be based on PKS and by the iscalimab treatment dose level a subject is most frequently exposed to, including the loading dose, during the study. Only data in the extension study will be included in the analysis.

Summaries of extension data in IMS will be based on the re-assigned treatment groups.

- CFZ533 600 mg
- CFZ533 300 mg

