2.5 Pharmacokinetic and immunogenicity endpoints

PK data will be analyzed in PK set by iscalimab treatment. To preserve blinding of treatment assignment, the PK data will be accessible to blinded personnel in the CTT only after unblinding for the primary analysis.

Trough free plasma concentration (C-trough in microg/mL) of iscalimab will be directly derived from the bioanalytical data and loaded into clinical database.

Time (days) elapsed since the first dose (Elapsed Time #1 with reference to the Dose Reference ID #1 – as defined in the Blood Log) of iscalimab will be derived (date of PK blood sampling – date of first dose of iscalimab treatment) + 1) and compared to the analysis windows defined in Table 2-1 to assign the values to analysis visits. If multiple measurements fall within the same analysis window, the algorithms outlined in Table 2-1 will be used to choose the value for the visit.

Also, with reference to the Dose Reference ID #2 (as defined in the Blood Log), Elapsed Time #2, the time (days) elapsed since the specified dose, will be derived and reported as well in the merged file.

Descriptive summaries of C-trough will be presented by iscalimab treatment and analysis visit. Summary statistics will include mean (arithmetic and geometric), SD, coefficient of variation (CV) (arithmetic and geometric), median, minimum and maximum. Concentrations below LLOQ will be treated as zero in summary statistics and the frequency (n, %) of concentrations below the LLOQ will be provided.

Trough plasma iscalimab concentrations overtime (elapsed time since first dose) for patients will be presented with spaghetti plots for each iscalimab treatment group. All concentration measurements will be plotted based on the actual day/time of assessment after the first dose date of iscalimab treatment.

A listing by cohorts, iscalimab treatment, patient number and CRF visit will also be produced.

The Ctrough,ss (steady state Ctrough) will be directly extracted from the bioanalytical data and summarized by iscalimab treatment groups for mean (arithmetic and geometric), SD, coefficient of variation (CV) (arithmetic and geometric), median, minimum and maximum.

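### The PK Set admits only participants with quantifiable iscalimab, so anyone below LLOQ at every sample leaves the trough and below-LLOQ summaries meant to count them

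*SAP*

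**What the plan says.** The SAP's Analysis sets section (after Section 2.1.1.7) defines the set: "The PK Set (PKS) includes all subjects who received at least one dose of iscalimab treatment and have quantifiable PK measurements of iscalimab". It adds: "Analysis of plasma PK, will be based on PKS". SAP Section 2.5 repeats the link: "PK data will be analyzed in PK set by iscalimab treatment".

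The same Section 2.5 treats results below LLOQ as data: "Concentrations below LLOQ will be treated as zero in summary statistics and the frequency (n, %) of concentrations below the LLOQ will be provided".

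The protocol has no matching restriction. Section 8.5.2 says that free iscalimab "plasma concentrations will be measured in all participants". Section 12.5.1 asks for summaries by dose level and visit, "including the frequency (n, %) of concentrations below the LLOQ". Protocol Section 12.1 defines only the Full Analysis Set and the Safety Set. SAP Section 3 lists one departure from the protocol, the wider TEAE definition, and does not mention the PK Set.

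**The concern.** Entry to the set depends on the outcome that the set is used to summarise. LLOQ is by definition the limit of quantification, so a dosed and sampled participant whose results are all BLQ has no quantifiable measurement and is not admitted. A participant with a single quantifiable result is admitted, and that person's BLQ results then count as zero. The plan therefore counts intermittent loss of exposure and discards complete loss of exposure.

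Trough level and the dose-exposure relationship form the first secondary objective (Protocol Table 2-1). The outputs affected are the arithmetic mean and the BLQ n (%) in each arm. The median and minimum can also rise.

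**Working it through.** **Inputs**
- Entry rule and BLQ handling: SAP Analysis sets and Section 2.5.
- Extension PK samples: Weeks 76, 92, 108/TD and 120/EOS (Protocol Table 16-5). None falls in the loading weeks. Week 120 is 14 weeks after the last dose at Week 106.
- Predicted steady-state troughs (Protocol Section 4.2): at 300 mg, median about 54 µg/mL, "90% of the population within 125 - 0.1" µg/mL; at 600 mg, median about 144 µg/mL, with 90% within 46 to 282 µg/mL.
- Not given: the LLOQ, the extension arm sizes (SAP Section 1.1 gives 206 in total), and how far BLQ persists within a person.

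**1. The plan's own figure.** The trough predictions are model output whose inputs are not in the documents, so they cannot be reproduced. Their shape can be checked, reading each range as the 5th to 95th percentile. Under a lognormal, the 5th percentile equals median² / 95th percentile.
- 300 mg: 54²/125 = 23.3 µg/mL, against the stated 0.1.
- 600 mg: 144²/282 = 73.5 µg/mL, against the stated 46.

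The protocol thus predicts a far heavier low tail at 300 mg than a lognormal would give, and a modest one at 600 mg.

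**2. Arithmetic mean.** Let f be the share of an arm that is BLQ at every sample, each counted as zero. With n participants and total concentration S at a visit, the mean over all sampled participants is S/n and the PK Set mean is S/[n(1−f)]. Inflation = 1/(1−f) − 1.
- f = 1%: 1/0.99 − 1 = 1.0%
- f = 2%: 1/0.98 − 1 = 2.0%
- f = 5%: 1/0.95 − 1 = 5.3%
- f = 0: no inflation

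**3. BLQ percentage.** If a share b is BLQ at a visit, the PK Set shows (b−f)/(1−f). Taking b = 5% as an assumption:
- f = 1%: 0.04/0.99 = 4.0%
- f = 2.5%: 0.025/0.975 = 2.6%
- f = 5%: 0/0.95 = 0%

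**4. Head count.** Expected exclusions are n × f. For an arm of 40 to 120 participants (assumed), f = 1% gives 0.4 to 1.2 people and f = 5% gives 2 to 6.

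**5. Dose contrast.** Dropping the lowest share f moves the median to the (0.5 + f/2) quantile. At f = 5% this is the 52.5th percentile of the predicted 300 mg distribution. A lognormal above the median gives 55.8 µg/mL. Straight-line interpolation gives 54 + (0.025/0.45) × (125 − 54) = 57.9 µg/mL. With 600 mg held at 144, the ratio of medians goes from 144/54 = 2.67 to between 144/57.9 = 2.49 and 144/55.8 = 2.58.

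**The case against.** **Quantifiable may have been meant as evaluable.** The IM Set uses the same template word, and Section 2.5 plainly expects BLQ values among the data it summarises. This reading is possible, but it is not what the text says, and a programmer following the text would exclude all-BLQ participants. If it was the intent, the correction is a clarification.

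**The entry rule does not say which samples count.** The limit to extension data is attached to the analysis, not to entry. All entrants should have had iscalimab in core Period 2, since the placebo arms were switched (Protocol Section 16.11). If an earlier quantifiable core result qualifies a participant, few or none would be lost. This stands as a second ambiguity for the definition to settle.

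**The 300 mg prediction may not apply here.** A reader might infer that about 5% of the extension 300 mg arm will be excluded and the 600 mg arm spared. The documents do not support that. The 5% refers to one steady-state time point. It equals f only if 0.1 µg/mL is at or below the LLOQ and the same people are BLQ at every sample. Protocol Section 6.1.3 also sends only core-study responders to 300 mg and moves 300 mg and 150 mg non-responders to 600 mg. If low exposure reduces response, some low-exposure participants will be in the 600 mg arm.

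**The two doses stay clearly apart.** A reader might also infer that the doses will look more alike than they are, or that lower percentiles will be distorted. Step 5 shows that the separation remains obvious even at f = 5%, and apart from the minimum Section 2.5 reports no lower percentile.

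**The data are not lost.** Protocol Section 12.5.1 lists concentrations by participant, and the Bioanalytical Data Report records BLQ results. That is so, but listings do not correct a summary table with the wrong denominator.

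**Conclusion.** The point holds as a defect in the set definition. Read literally, the SAP removes always-BLQ participants from the very summaries that count BLQ as zero and report its frequency, and it does so without a basis in the protocol or a declared change. The direction is fixed: the arithmetic mean can only rise and the BLQ percentage can only fall.

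The size cannot be determined, because the LLOQ, arm sizes and persistence of BLQ are not given. For assumed f of 2% and 5% the mean is inflated by 2.0% and 5.3%. The BLQ percentage is more sensitive: an assumed 5% would appear as anything from 4.0% to 0% as f goes from 1% to 5%. If nobody is always BLQ, or if core-study results qualify people for entry, the effect may be nil. The protocol's prediction makes 300 mg the arm mainly at risk, but does not establish how many people would be affected there. The matter is worth correcting because a planned output can be biased and the remedy is cheap.

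**What to change.** Redefine the PK Set as all participants with at least one extension dose and at least one valid (evaluable) post-dose extension concentration, including results below LLOQ. Report BLQ n (%) by visit and arm on that set. List the set definition in SAP Section 3, since the protocol does not define a PK set.

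Optionally, add n (%) with trough at or above 40 µg/mL, the threshold in Protocol Section 4.2. For any LLOQ below 40 µg/mL this row does not depend on how BLQ values are imputed. It is an addition and is not needed for the correction.

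The cost is one reworded sentence, one line in Section 3 and, if wanted, one table row. No new samples or data are needed. The only consequence is that exposure may look slightly lower in an arm that contains always-BLQ participants.

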There is a hypothetical risk for thromboembolic complications when targeting this co-stimulatory pathway. This risk is based on clinical results from previous compounds (e.g. BG9588, IDEC-131) which have targeted CD154 (CD40 ligand) and resulted in a fatal hyper-coagulation phenotype.

Although the risk is theoretical, hematologic and coagulation parameters will be monitored in the current study. Furthermore, participants with conditions such as antiphospholipid syndrome, who are at a higher risk for thromboembolism, will be excluded unless they are receiving antithrombotic prophylaxis. CFZ533 binds to CD40 receptor and is Fc-silent mAb hence does not appear to carry the same risk of thrombosis. Both preclinical and clinical data from an extensive Phase 2 clinical program across healthy subjects and participants across different indications have not indicated a risk of thrombosis with CFZ533.

Risk 4 Immunogenicity

As with any monoclonal antibody, there is a hypothetical risk of developing anti-CFZ533 antibodies. However, it is likely that CFZ533 doses will achieve complete receptor occupancy during the treatment period. In these conditions, it is expected that CFZ533 will retain its capacity to block immune responses, including those directed against the drug itself, neutralizing or not.

Samples will be collected during study to assess immunogenicity. Immunogenicity will be monitored during clinical development and the consequences of an immune response to CFZ533 could be correlated with, a loss of exposure (PK), a loss of peripheral CD40 receptor occupancy (PD), and/or the appearance of immune related adverse events including injection site reactions.

Risk 5 Vaccination Failure

Vaccination of participants during treatment with CFZ533 and prior to clearance of the antibody is likely to result in therapeutic failure (i.e., non-protective antibody titers) due to the pharmacologic activity of the antibody. Administration of live attenuated vaccines should be avoided while receiving CFZ533 treatment and for at least 14 weeks thereafter.

One fatal event (potential CMV infection) was reported in the CCFZ533X2202 clinical trial in Lupus nephritis, suspected to be related to the study medication by the Investigator.

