8.5.3 Immunogenicity

The presence of anti-CFZ533 (iscalimab) antibodies will be determined in all participants, using a validated assay.

All blood samples will be taken by either direct venipuncture or an indwelling cannula inserted in a forearm vein. Details of sample processing, handling, storage and shipment will be described in a separate laboratory manual.

All samples will be given a unique sample number as listed in the [Section 16.5](#). The data and details of the analytical methods will be provided in a standalone Bioanalytical Data Report.

[REDACTED]

[REDACTED]

[REDACTED]

9 Study discontinuation and completion

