Immunogenicity results will be listed by treatment arm, subject, and visit for subject who received at least one dose of iscalimab. Incidence of anti-drug antibody positive subjects (ADA+) may be calculated by iscalimab dose level and analysis visit defined based on time since first dose of iscalimab. Subjects' data from both cohorts will be pooled according to the iscalimab dose levels.

•

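### The SAP names two analysis sets for anti-drug antibody (ADA) incidence, and the one it prescribes can drop ADA-positive participants who have lost exposure

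*SAP*

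**What the plan says.** Four places in the SAP bear on who is counted.

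- **Analysis sets, PK Set.** Membership needs at least one dose, and participants must "have quantifiable PK measurements of iscalimab".
- **Analysis sets, IM Set.** Membership needs at least one dose, and participants must "have quantifiable immunogenicity measurements of iscalimab". There is no PK condition.
- **Same IM Set paragraph.** The next sentence reads "Analysis of immunogenicity data will be based on PKS and by the iscalimab treatment dose level a subject is most frequently exposed to". The paragraph then closes with "Summaries of extension data in IMS will be based on the re-assigned treatment groups".
- **Section 2.5.** "Immunogenicity results will be listed by treatment arm, subject, and visit for subject who received at least one dose of iscalimab". For the summary: "Incidence of anti-drug antibody positive subjects (ADA+) may be calculated by iscalimab dose level and analysis visit". No analysis set is named for that incidence.

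The protocol defines only the FAS and the Safety Set (12.1) and gives no immunogenicity population in 12.5.3. Under 8.5.3, anti-drug "antibodies will be determined in all participants, using a validated assay". Table 2-1 makes ADA incidence at analysis visits the endpoint for the second of the two secondary objectives.

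**The concern.** One paragraph gives two answers to the question of which set is used, and the two sets have different entry conditions. Two programmers could produce different ADA percentages from the same data, each with text to support the choice.

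The PKS reading has a further problem. Membership depends on measurable drug after treatment has started, and measurable drug may itself depend on the outcome being counted. Protocol 4.5 (Table 4-1, Risk 4) lists loss of exposure among the things with which an immune response to the drug could be correlated. A participant whose antibodies clear the drug could therefore be removed from the incidence because of those antibodies.

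A second, smaller ambiguity sits in the IMS definition. ADA incidence rests on a positive or negative result, and the word 'quantifiable' does not say whether a valid negative qualifies.

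**Working it through.** The plan gives no figure for this point: no assumed ADA rate, no assay limit and no power calculation. The check is therefore a comparison of passages, followed by an illustration on stated assumptions.

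**1. Would a dropped participant have ADA data?** Yes. The blood logs (Protocol 16.5) schedule PK samples at Weeks 76, 92, 108/TD and 120, and ADA samples at the same four visits. ADA is determined in everyone. The exclusion is therefore not caused by missing ADA results.

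**2. Who is dropped?** One quantifiable PK sample is enough to stay in the PKS. Only participants below the limit of quantification at every available sample leave it. Completers have four scheduled chances. A participant who stops before Week 76 has only the TD and Week 120/EOS samples. For completers, Week 120 is 14 weeks after the last dose at Week 106, when the protocol expects concentrations to have fallen (4.2). In the 300 mg arm the expected 90% range of steady-state troughs reaches down to 0.1 µg/mL, against 46 µg/mL at 600 mg (4.2), so any exclusion may fall unevenly between the dose levels by which incidence is reported.

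**3. Effect on the incidence.** Let p be the true ADA incidence, a the share of ADA-positives with no quantifiable PK sample, and b the same share among ADA-negatives. All three are assumptions.

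Incidence in PKS = p(1 − a) / [p(1 − a) + (1 − p)(1 − b)]

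This is below p when a > b, equal to p when a = b, and above p when a < b.

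| p | a | b | Calculation | PKS incidence |
|---|---|---|---|---|
| 5% | 5% | 5% | 0.0475 / (0.0475 + 0.9025) | 5.00% |
| 5% | 0 | 5% | 0.05 / (0.05 + 0.9025) | 5.25% |
| 5% | 10% | 5% | 0.045 / (0.045 + 0.9025) | 4.75% |
| 5% | 25% | 2% | 0.0375 / (0.0375 + 0.931) | 3.87% |
| 5% | 50% | 2% | 0.025 / (0.025 + 0.931) | 2.62% |
| 10% | 5% | 5% | 0.095 / (0.095 + 0.855) | 10.00% |
| 10% | 0 | 5% | 0.10 / (0.10 + 0.855) | 10.47% |
| 10% | 50% | 2% | 0.05 / (0.05 + 0.882) | 5.36% |

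**4. The same in counts.** SAP 1.1 gives 206 enrolled. Assume all were dosed and tested, and that no ADA-negative participant is dropped.

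- 4 positives: 4/206 = 1.9%. Dropping one gives 3/205 = 1.5%; dropping two gives 2/204 = 1.0%.
- 10 positives: 10/206 = 4.9%. Dropping two gives 8/204 = 3.9%; dropping five gives 5/201 = 2.5%.
- 21 positives: 21/206 = 10.2%. Dropping five gives 16/201 = 8.0%.

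With few positives, one or two exclusions visibly change the percentage. If no positive is dropped, nothing changes under these assumptions.

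**The case against.** The strongest reply is that this is a drafting slip whose intent can be recovered. The disputed sentence repeats the PK Set wording, sits inside the IMS definition and, taken literally, leaves the IMS without a use. SAP 2.5 assigns the PK set to PK data and does not invoke it for immunogenicity. That is probably right. It does not settle the matter, because SAP 2.5 still names no denominator and the sentence remains an operative rule for a secondary endpoint.

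A second reply is that 'quantifiable' may mean only evaluable in both definitions, in which case the two sets nearly coincide. That reading is possible. For PK, however, SAP 2.5 uses a lower limit of quantification and counts values below it, so the stricter reading is the natural one there.

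Third, the affected group is narrow, and the larger scenarios need many ADA-positives to lose drug at every sample. The protocol calls the ADA risk hypothetical and expects the drug to suppress responses to itself. This stands: the table shows the range, not a forecast, and a milder case (a = 10%, b = 5%) moves 5% only to 4.7%.

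Fourth, the direction is not certain. Protocol 4.2 attributes variability in exposure to CD40 biology, which could also remove ADA-negatives. If that is unrelated to ADA status, it removes both groups at the same rate and adds no bias. Overstatement needs negatives to be lost at a higher rate than positives.

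Finally, the analysis is descriptive, the incidence is worded as optional, and the listing of all dosed participants would still show every excluded result. All of that limits the damage to the summary percentage.

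**Conclusion.** The concern holds. The SAP contradicts itself on the population for ADA incidence, and nothing elsewhere in either document resolves it. Followed as written, the PKS rule can remove participants with valid ADA results for a reason the protocol links to the outcome. Understatement is the more plausible direction, but it is conditional on ADA-positives being lost at a higher rate than ADA-negatives. The size cannot be derived from the documents; across the scenarios assumed here, a true 5% would be reported as anything from 2.6% to 5.2%. This should be corrected before analysis. It affects no primary endpoint, sample size or stopping rule.

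**What to change.** Three wording changes in the SAP:

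1. In the IM Set paragraph, replace PKS with IMS in the sentence that assigns the analysis set.
2. Define the IMS as all participants with at least one extension dose and at least one valid (non-missing) post-dose ADA result, positive or negative, in place of 'quantifiable'.
3. In SAP 2.5, name the IMS as the population for ADA incidence, with the denominator at each visit being those with a valid result at that visit.

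The first change removes the contradiction. The other two ensure that the corrected text gives a single denominator. The cost is an edit to the Analysis sets text and to SAP 2.5, with no new sampling or data collection.
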